2.2 STUDY OBJECTIVES

- **Primary objective**
 - *To evaluate the effectiveness of atorvastatin in Chinese cardiology patients in real world setting.*
- **Secondary objectives**
 - *To assess atorvastatin safety in cardiology patients in real world setting*
 - *To analyze patterns of atorvastatin prescription in cardiology patients*

2.3 SAMPLE SIZE AND POWER CALCULATIONS

In the recently published DYSIS [1] study, the achievement rate of Low-Density Lipoprotein Cholesterol (LDL-C) value was about 60% among Chinese outpatients taking 3 months lipid-lowering therapy. In this NI study, we assumed the achievement rate of LDL-C of 60%, allowable error rate of 1.1 %, type I error of 0.05, we calculated a required sample size of 7600 patients. Considering 24% loss to follow-up in real-world setting, the sample size will be 10,000.

This sample size will also allow for stratification by sex, age (<65 years vs \geq 65 years), risk stratification (very high risk, high risk, moderate risk and low risk) and baseline disease type (with established CHD, having multiple risk factors, and primary hypercholesterolemia).

3 INTERIM ANALYSES

No interim analysis is planned.

4 HYPOTHESES AND DECISION RULES

4.1 STATISTICAL HYPOTHESES

There are no formal hypotheses specified for the study.

4.2 STATISTICAL DECISION RULES

Not applicable.

5 ANALYSIS SETS/ POPULATIONS

5.1 FULL ANALYSIS SET (FAS)

The FAS analysis population will include all enrolled in the study that received at least one dose of atorvastatin and completed 12- week follow-up. The FAS population will be the primary analysis set for the primary endpoint.

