#### 8.1.2. Study Endpoint

- **Primary endpoint**

- Achievement rate of LDL-C goals at 12 weeks of therapy of Atorvastatin according to Chinese Guideline on Dyslipidemia Prevention and Treatment in Adult (2007 version). It will be presented with the proportion of patients who achieve the LDL-C goal value. LDL-C target value for the patients with different risk level is defined in the [section 8.2.5](#) per guideline.

$$\text{Achievement Rate} = \frac{\text{No. subjects who achieve LDL-C target value}}{\text{No. subjects who complete 12-week follow up}}$$

- The time of 12-week will be calculated from the day when each patient starts taking atorvastatin. .
- Achievement rate will be summarized overall, within each risk strata, and by dose within each risk strata. 95% confidence intervals will be provided.

- **Secondary endpoint**

- Dosage distribution of Atorvastatin in cardiology patients with different risk stratification at the end of 12-week follow-up
- Safety and tolerability will be evaluated by recording the incidence and severity of adverse events, abnormal physical examination findings, and abnormal laboratory values through 12 weeks of treatment. Especially monitoring the patients who have any the following events:
  - Having muscle symptoms such as myalgia, fatigue, weakness, creatine kinase values 10 times the upper limit of normal, or rhabdomyolysis,
  - Having persistent elevation in alanine aminotransferase, aspartate aminotransferase, or both (defined as two consecutive measurements obtained 4 to 10 days apart that is more than three times the upper limit of the normal range).

- Major adverse cardiovascular events will also be recorded as adverse events, including death, myocardial infarction, stroke, documented unstable angina requiring re-hospitalization, revascularization with either percutaneous coronary intervention or coronary-artery bypass grafting.

Adverse events will be summarized overall and by dose within each risk strata.

- Dropout percentage and reason through 12 weeks of follow-up;

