#### **8.5. Study Size**

- The NI study is designed to detect the achievement rate of LDL-C value in cardiology patients with atorvastatin therapy in real world setting. The length of follow-up is designed to be 12 weeks.
- In the recently published DYSIS  study, the achievement rate of LDL-C value was about 60% among Chinese patients taking 3 months lipid-lowering therapy. In this NI study, we assumed the achievement rate of LDL-C of 60%, allowable error rate of 1.1%, type I error of 0.05, we calculated a required sample size of 7600 patients. Considering 24% loss to follow-up in real-world setting, the sample size will be 10,000. This sample size will also allow for stratification by sex, age ( $\geq 65$  years), risk stratification (very high risk, high risk, moderate risk and low risk) and baseline disease type (with established CHD, having multiple risk factors, and primary hypercholesterolemia).

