2.1 STUDY DESIGN

Overview

This is a multi-center, prospective, observational study, which will be completed by Beijing Anzhen Hospital, Capital Medical University and approximately 64 other clinical sites.

At baseline visit, patient inclusion/exclusion and demographic information, medical history, medication records, concomitant drugs and laboratory examination results prior to atorvastatin therapy such as liver function, blood lipid parameter, creatine kinase value and renal function will be collected by investigators in the study. At week 12 visit and any unplanned visits, the laboratory examination results and medication records will be collected. Adverse events will be recorded at any time during the study period. Schedule of Activities is as follows:

Table 1: Schedule of Activities

Visits	Visit 1	Visit 2	Any unplanned visits
Protocol Activity	Baseline Day 1	Week 12 Day 85 (± 28 days)	Any Date During Week 4 to Study Close
Signed Informed Consent Form	▲		
Demographic information	▲		
Medical history	▲		
Laboratory examination	▲*	▲	▲
Inclusion/exclusion criteria	▲		
Adverse event records	Record at any time during the study period		
Medication records	▲	▲	▲

* The date of the report should be within 1 month before taking atorvastatin.

Study population

Judged by investigators, patients in cardiology department who are eligible for inclusion and exclusion criteria can be included into this study. Estimated total sample size is 10,000 and will be conducted in approximately 65 hospitals in China.

Data source

This Non-Interventional (NI) study data will be recorded in the medical records by investigators, and then input to electronic Data Collection (EDC) system as the form of electronic Case Report Form (eCRF).

Treatment/dose group

The study drug (atorvastatin) is from the doctor's prescription and will be recorded on Day 1, Week 12, and within Week 4 to end of the study. The analysis by dose groups will be taken the dose level recorded at Week 12 (Visit 2) on the prescription level or the last dose in the unplanned visit if the Week 12 is not available.

The dose groups will be in four daily dose levels, 10 mg, 20 mg, 40 mg and > 40 mg.

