5.4 SUBGROUPS

Primary and secondary endpoints described in Section 6 will be summarized descriptively in all analysis populations except EP in these subgroups.

- **Age at Baseline**
 - 18 – 64 years old
 - ≥ 65 years old
- **Dose Groups**

The dose groups will be in four Atorvastatin daily dose levels:

- 10 mg
- 20 mg
- 40 mg
- > 40 mg

- **Baseline Variables**

Subgroup analyses may be performed within the following categories.

- CVD risk level: low, moderate, high, very high, per definition in [Table 2](#).
- Disease type: established CHD (Coronary Heart Disease), multiple risk factors, and hypercholesterolemia

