7 HANDLING OF MISSING VALUES

For all endpoints, individual missing data will not be imputed.

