8 STATISTICAL METHODOLOGY AND STATISTICAL ANALYSES

8.1 STATISTICAL METHODS

SAS[®] Version 9.4 or later will be used to produce all listings and summary tables.

Summary tables presented by visit will include results from scheduled visits such as Day 1 and Week 12. Unscheduled visits will be listed but not summarized except in the event that an unscheduled result qualifies as a baseline result or other derived endpoint.

- **Analyses for Continuous Data**

Summary statistics for continuous variables/endpoints will be presented with number of observations (n), mean, SD, median, minimum (min), and maximum (max).

- **Analyses for Categorical Data**

Summary statistics for categorical variables/endpoints will be presented with number of observations (n) and percentages.

- **Analyses for Binary endpoints**

Exact methods (Clopper-Pearson Interval) will be used to calculate confidence interval (CI) for the primary (efficacy) endpoint: achievement rate of LDL-C at Week 12.

$$\left[\frac{r}{r + (n - r + 1)F_{1-\alpha/2;2(n-r+1),2r}}, \frac{(r + 1)F_{1-\alpha/2;2(r+1),2(n-r)}}{(n - r) + (r + 1)F_{1-\alpha/2;2(r+1),2(n-r)}} \right]$$

Where r is the proportion of patients who met therapy target level and n is the total number of patients who completed 12-weeks.

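### The primary LDL-C rate describes 12-week completers only, with 24% loss allowed for and no all-treated rate or missing-data bounds planned

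*SAP*

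**What the plan says.** The restriction to completers is consistent across both documents:

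- Protocol 8.1.2 and SAP 6.1 define the achievement rate with the denominator "No. subjects who complete 12-week follow up".
- SAP 5.1 limits the FAS to "all enrolled in the study that received at least one dose of atorvastatin and completed 12- week follow-up", and SAP 8.2 runs the primary analysis in that set.
- SAP 8.1 sets up the Clopper-Pearson interval so that "n is the total number of patients who completed 12-weeks".

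The sample size expects many patients not to reach that point. Protocol 8.5 says: "Considering 24% loss to follow-up in real-world setting, the sample size will be 10,000". SAP 2.3 repeats this.

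On missing data, SAP 7 says only: "For all endpoints, individual missing data will not be imputed". SAP 5.4 adds: "Primary and secondary endpoints described in Section 6 will be summarized descriptively in all analysis populations except EP in these subgroups". That brings in the Safety set, which SAP 5.2 defines as everyone with at least one dose.

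Several provisions reduce the problem. SAP 1 and Appendix 1 widen the Week 12 window to Day 85 ± 28. SAP 8.1 lists unscheduled results without summarising them, "except in the event that an unscheduled result qualifies as a baseline result or other derived endpoint". SAP 6.2 and 8.2 tabulate how many patients drop out and why. For the dose group, SAP 2.1 gives an explicit fallback: "or the last dose in the unplanned visit if the Week 12 is not available". It gives none for LDL-C.

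**The concern.** The primary objective (Protocol 7.1) is how well atorvastatin works in routine cardiology practice in China. The headline rate answers a narrower question: how often patients who reach the Week 12 assessment are at goal. If patients who do not return differ in goal attainment from those who do, the two rates differ. The planned interval does not show this, because it reflects sampling error among completers only.

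The study has no hypothesis test and no decision rule, so the estimate itself is the product. It was sized to be precise to 1.1 percentage points. If a modest difference in the missing quarter of patients can move it that far, readers should be shown how far the result depends on them.

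A smaller gap lies inside the primary rate. A completer with no Week 12 LDL-C value stays in the denominator under the SAP 6.1 formula, and so in effect counts as not at goal. Under one reading of the no-imputation rule in SAP 7, the same patient is left out. Two programmers could follow the SAP and report different rates.

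**Working it through.** **Inputs.** Attainment 60%, allowable error 1.1 points, type I error 0.05, 7,600 evaluable, 24% loss and 10,000 enrolled all come from Protocol 8.5 and SAP 2.3. I take all 10,000 as treated (assumption).

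**1. The plan's own figure.** n = 1.96² × 0.60 × 0.40 / 0.011² gives 7,620 after rounding up, against 7,600 stated (0.3% apart). Then 7,600 / (1 − 0.24) = 10,000. The half-width at 7,600 is 1.96 × √(0.60 × 0.40 / 7,600) = 0.0110. The sample size reproduces. With 0.60 × 7,600 = 4,560 at goal, the Clopper-Pearson interval is 58.9% to 61.1%.

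**2. What the Safety-set summary would show.** SAP 5.4 refers to the endpoints of Section 6. Section 6.1 fixes the denominator as completers, and SAP 7 imputes nothing. Safety-set patients who completed 12 weeks are treated completers, which is the FAS. Read literally, the Safety-set rate therefore equals the FAS rate. If the whole Safety set was meant as the denominator, that departs from 6.1, and SAP 7 does not say whether a missing LDL-C then counts as not achieved.

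**3. All-treated rate.** With loss L and attainment q among non-completers, rate = (1 − L) × 0.60 + L × q. At L = 0.24:

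| q (assumed) | All-treated rate | Shift from 60% |
|---|---|---|
| 0% (lower extreme) | 45.6% (4,560/10,000) | −14.4 |
| 50% | 57.6% | −2.4 |
| 55% | 58.8% | −1.2 |
| 65% | 61.2% | +1.2 |
| 70% | 62.4% | +2.4 |
| 100% (upper extreme) | 69.6% (6,960/10,000) | +9.6 |

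The gap that shifts the rate by the full half-width is 1.1 / 0.24 = 4.6 points.

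**4. Other loss rates (assumptions).** The bounds are 0.60 × (1 − L) and 0.60 × (1 − L) + L. They give 54% to 64% at L = 10%, 51% to 66% at 15%, and 42% to 72% at 30%. At 10% loss, the gap needed for a 1.1-point shift is 1.1 / 0.10 = 11 points.

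**5. Effect of in-window unplanned values (assumptions).** Suppose a share f of non-completers has an LDL-C value in the window, with 60% of these at goal. The share still missing is 0.24 × (1 − f). For f = 25% it is 0.18 and the bounds are 49.2% to 67.2%. For f = 50% it is 0.12 and the bounds are 52.8% to 64.8%.

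**6. Completers without LDL-C.** With 60% among those measured and a share m unmeasured, the SAP 6.1 formula gives 0.60 × (1 − m), against 60% if they are left out. A 1.1-point difference needs m = 0.011 / 0.60 = 1.8%, about 140 of 7,600. The documents give no value for m.

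**The case against.** The best defence is that the plan is open about what it estimates. The completer denominator is stated consistently, the study is single-arm and descriptive, and no decision rests on the rate. The 24% is a planning allowance, and the wider window was adopted to keep more patients in the analysis. SAP 8.3 reports the size of each population, and SAP 8.2 gives dropout with reasons by dose group within risk level. A reader could therefore work out crude overall bounds from the numbers at goal, completing and treated.

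Much of this stands. It also rules out several stronger readings that a reader might infer:

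- *That the Safety-set summary has no denominator or missing-data rule.* It has both, through SAP 6.1 and SAP 7. The difficulty is that they lead back to the FAS rate.
- *That completion is left wholly undefined.* Protocol 8.2.6 separates finishing all visits from withdrawal, Protocol 8.2.7 schedules Visit 2 with laboratory tests, and SAP Appendix 1 gives the Week 12 window. The meaning can largely be read from these.
- *That unplanned LDL-C values are shut out.* Appendix 1 works from the assessment date and does not tie Week 12 to Visit 2, and SAP 8.1 lets an unscheduled result serve a derived endpoint. In-window values are arguably already admitted, although goal attainment is not named.
- *That the completer rate flatters the drug.* Nothing in the documents fixes the direction for non-completers.

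What the defence does not supply is an all-treated rate. Bounds worked out by a reader would not use in-window values from non-completers. They would also depend on how completers without LDL-C were counted.

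**Conclusion.** The concern holds, and the point should be fixed. The primary rate and its interval describe completers only. The Safety-set summary, read literally, repeats that rate, and no analysis shows how far the result depends on patients without a Week 12 value.

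At 60% attainment and 24% loss, a 4.6-point gap between non-completers and completers is worth the full 1.1-point half-width. The extreme bounds run from 45.6% to 69.6%, or from 54% to 64% if loss is 10% (assumption). A reader might take 45.6% as the real-world rate. The documents do not support that, because it needs every lost patient to be off goal. The size depends on actual loss, which may be below 24% with the ± 28-day window.

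The unclear counting of completers without LDL-C is a lesser matter. Visit 2 includes laboratory tests, so the number affected may be small.

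**What to change.** Keep the protocol formula in the FAS as the primary analysis, and make these SAP changes before data lock:

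- **SAP 5.4 and 8.2:** add a supportive achievement rate with all Safety-set patients as the denominator, overall and by risk stratum. Use any LDL-C value within Day 85 ± 28, including values from unplanned visits, and state which value is taken if several fall in the window. Then count the remaining missing values once as not achieved and once as achieved, and label the two results as lower and upper bounds.
- **SAP 7:** add an exception for these bounds, so that they do not contradict the no-imputation rule.
- **SAP 6.1:** add one sentence on whether a completer without LDL-C stays in the denominator.

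The cost is a few lines of SAP text and a small number of tables from data already collected. The primary estimate keeps its definition. The drawback is that the bounds will be wide, rest on deliberately extreme assumptions, and may look less favourable than the primary rate, so the report should present them as limits.

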5.2 SAFETY ANALYSIS SET (SAS)

The Safety Analysis population will include all patients who receive at least one dose of study drug atorvastatin. The SAS will be the primary analysis population for all safety reporting.

5.3 ENROLLED POPULATION (EP)

The enrolled population will consist of all patients who signed informed consent.

5.4 SUBGROUPS

Primary and secondary endpoints described in Section 6 will be summarized descriptively in all analysis populations except EP in these subgroups.

- **Age at Baseline**
 - 18 – 64 years old
 - ≥ 65 years old
- **Dose Groups**

The dose groups will be in four Atorvastatin daily dose levels:

- 10 mg
- 20 mg
- 40 mg
- > 40 mg

- **Baseline Variables**

Subgroup analyses may be performed within the following categories.

- CVD risk level: low, moderate, high, very high, per definition in [Table 2](#).
- Disease type: established CHD (Coronary Heart Disease), multiple risk factors, and hypercholesterolemia

6 ENDPOINTS AND COVARIATES

6.1 PRIMARY (EFFICACY) ENDPOINT

- *The primary efficacy endpoint is the proportion of patients who achieve the LDL-C goal value. Achievement rate of LDL-C goals at 12 weeks of therapy of atorvastatin are evaluated according to Chinese Guideline on Dyslipidemia Prevention and Treatment in Adult (2007 version).*

$$\text{Achievement Rate} = \frac{\text{No. subjects who achieve LDL-C target value}}{\text{No. subjects who complete 12-week follow up}}$$

The Chinese Guideline on Dyslipidemia Prevention and Treatment in Adult (2007), the Cardiovascular Disease (CVD) risk stratification and LDL-C therapy target value are defined in Table 2.

Table 2: CVD Risk Stratification and LDL-C Therapy Target Value

Risk stratification	Beginning of drug therapy	Therapy target value
Low-risk: 10 years CV risk <5%	LDL-C \geq 4.92 mmol/L (190mg/dl)	LDL-C < 4.14 mmol/L (160mg/dl)
Medium/ Moderate risk: 10 years CVD risk 5% - 10%	LDL-C \geq 4.14 mmol/L (160mg/dl)	LDL-C < 3.37 mmol/L (130mg/dl)
High risk: CHD or CHD risk equivalents, or 10 years CV risk 10% - 15%	LDL-C \geq 2.59 mmol/L (100mg/dl)	LDL-C < 2.59 mmol/L (100mg/dl)
Very high risk: acute coronary syndromes, or ischemic cardiovascular disease combined with diabetes	LDL-C \geq 2.07 mmol/L (80mg/dl)	LDL-C < 2.07 mmol/L (80mg/dl)

Target achievement rate will be summarized overall, within each risk strata, and by dose within each risk strata. 95% confidence intervals will be provided.

6.2 SECONDARY ENDPOINTS

- Lipid parameters (LDL-C, *High-Density Lipoprotein Cholesterol* (HDL-C), Total Cholesterol (TC), and Triglycerides (TG)) at week 12, change from baseline in lipid parameters, and %change from baseline in lipid parameters at week 12, overall, and by CVD risk group.
- *Dosage distribution of atorvastatin in patients by CV risk stratification at the end of 12-week follow-up defined as follows:*

- The atorvastatin total dose in each patient will be calculated from Day 1 to Week 12/or last dose day.
- The patient daily dose will be the total dose divided by the total days of receiving atorvastatin.
- The Week 12 dose will be the dose taken at Week 12.

- **Duration on Study**

Duration on treatment group for each subject will be calculated as last treatment day – first dose date +1

- **Adverse Events**

Any new findings or worsening of findings at post-baseline visits will be reported as adverse events.

An adverse event is considered treatment emergent relative to a given treatment if:

- the event occurs for the first time during the effective duration of treatment and was not seen prior to the start of treatment, or
- the event was seen prior to the start of treatment but increased in severity during treatment.

- **Adverse Events Special Interest (AESI)**

The Adverse Events Special Interest (AESI) will be categorized as below:

- Muscle symptoms: myalgia, fatigue, weakness, creatine kinase values 10 times the upper limit of normal, or rhabdomyolysis, and muscle damage based on significant elevated creatine kinase (CK)
- Major cardiovascular events: myocardial infarction, stroke, unstable angina requiring re-hospitalization, revascularization with either percutaneous coronary intervention or coronary-artery bypass grafting
- Death

- **Abnormal Laboratory Data**

The following elevated abnormal laboratory data will be summarized.

- Significant elevated CK: CK values 10 times the upper limit of normal,
-
-

- Persistent elevation in alanine aminotransferase, aspartate aminotransferase, or both: two consecutive measurements obtained 4 to 10 days apart that is more than three times the upper limit of the normal range
- **Dropout**
Dropout percentages and reason through 12 weeks of follow-up

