## **DEFINITIONS OF SAFETY EVENTS**

### **Adverse events**

An AE is any untoward medical occurrence in a patient administered a medicinal product. The event need not necessarily have a causal relationship with the product treatment or usage. Examples of adverse events include but are not limited to:

- Abnormal test findings (see below for circumstances in which an abnormal test finding constitutes an adverse event);
- Clinically significant symptoms and signs;
- Changes in physical examination findings;
- Hypersensitivity;
- Progression/worsening of underlying disease;
- Lack of efficacy;
- Drug abuse;
- Drug dependency.

Additionally, for medicinal products, they may include the signs or symptoms resulting from:

- Drug overdose;
  - Drug withdrawal;
  - Drug misuse;
  - Off-label use;
  - Drug interactions;
  - Exposure during pregnancy;
  - Exposure during breast feeding;
  - Medication error
  - Occupational exposure.
- ;

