#### Abnormal test findings

The criteria for determining whether an abnormal objective test finding should be reported as an adverse event are as follows:

- Test result is associated with accompanying symptoms, and/or
- Test result requires additional diagnostic testing or medical/surgical intervention, and/or
- Test result leads to a change in study dosing or discontinuation from the study, significant additional concomitant drug treatment, or other therapy, and/or
- Test result is considered to be an adverse event by the investigator or sponsor.

Merely repeating an abnormal test, in the absence of any of the above conditions, does not constitute an adverse event. Any abnormal test result that is determined to be an error does not require reporting as an adverse event.

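### SAP 6.2 makes any new or worsened post-baseline finding an adverse event, which conflicts with the protocol's criteria for abnormal tests and could inflate adverse event incidence if applied literally

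*SAP*

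**What the plan says.** SAP 6.2, under Adverse Events, gives the rule: "Any new findings or worsening of findings at post-baseline visits will be reported as adverse events". It sets no threshold, adds no clinical qualifier and does not refer to the protocol's criteria. The definition of treatment emergence that follows concerns timing and worsening only.

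Protocol section 10 treats test results differently. Its general definition lists them with a restriction: "Abnormal test findings (see below for circumstances in which an abnormal test finding constitutes an adverse event". The subsection on abnormal test findings then begins "The criteria for determining whether an abnormal objective test finding should be reported as an adverse event are as follows" and gives four alternatives, any one of which is enough:

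- the patient has symptoms along with the abnormal result;
- the result calls for more diagnostic work or for treatment, medical or surgical;
- the result causes dosing to be altered, the patient to leave the study, or substantial further therapy to be given;
- the result is so judged, in the protocol's words: "Test result is considered to be an adverse event by the investigator or sponsor".

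The subsection closes with an exclusion: "Merely repeating an abnormal test, in the absence of any of the above conditions, does not constitute an adverse event".

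**The concern.** The incidence and severity of adverse events is a named secondary endpoint (protocol 8.1.2). SAP 8.2 tabulates adverse events by system organ class and preferred term, overall and by dose group within each risk stratum. The reader of those tables needs to know which rule produced the counts.

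Take an asymptomatic uric acid value that is newly out of range and prompts no action. Under the SAP sentence it is an adverse event. Under the protocol it is not, unless the investigator or sponsor judges it to be one. For test results the SAP rule contains everything the protocol rule does and more, so it can only add events. It also gives patients with more laboratory draws more chances to be counted.

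**Working it through.** The documents state no adverse event rate and no rate of out-of-range results, so there is no figure of the plan's to reproduce. The check is a comparison of the texts, followed by an illustration on assumed rates.

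**1. Does the SAP sentence reach laboratory values?** Protocol section 10 uses the word findings for test results. Protocol 8.2.7 says that the Week 12 visit and any unplanned visits collect laboratory results and medication records, with adverse events recorded throughout. The schedule of activities has no row for physical examination. Most of what a post-baseline visit can newly find is therefore a laboratory value.

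**2. Does anything in the SAP bring the protocol criteria back?** No. SAP 6.2 does not cite them, and the derivation appendix is silent on adverse events. The SAP's list of changes from its previous version concerns only the Week 12 window.

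**3. Which document prevails?** The SAP introduction says that the SAP supplements the protocol, which favours section 10. Protocol 8.7 says that the SAP may modify the protocol's plans and calls for an amendment only for major changes to the primary endpoint or its analysis. The SAP wording on a secondary endpoint could therefore be taken as the operative rule for analysis. The SAP introduction also says that deviations from the SAP will be described in the study report, so setting the sentence aside would itself need explaining.

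**4. Illustration of size.**

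- Analytes (protocol 8.3): ALT, AST, total bilirubin, CK, creatinine, BUN and uric acid, so k = 7. The four lipids are left out because the drug is expected to improve them.
- Chance q that an analyte is newly out of range at a visit: assumed 1%, 2.5% or 5%.
- Analytes assumed independent.
- Formula: P(at least one) = 1 − (1 − q)^k. For two visits, also taken as independent, the exponent is 14.

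| q | One visit | Two visits |
|---|---|---|
| 1% | 1 − 0.99^7 = 6.8% | 1 − 0.99^14 = 13.1% |
| 2.5% | 1 − 0.975^7 = 16.2% | 1 − 0.975^14 = 29.8% |
| 5% | 1 − 0.95^7 = 30.2% | 1 − 0.95^14 = 51.2% |

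Per 10,000 patients, the one-visit figures are about 680, 1,620 and 3,020. Under the SAP sentence read literally, all of these patients would have an adverse event. Under section 10, none would unless a criterion were met. Positive correlation lowers the figures. At the extreme of complete dependence, the one-visit probability falls to q itself, 1% to 5%. The two-visit column shows why patients with unplanned visits would be counted more often.

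**The case against.** The strongest reply is that the sentence would have no effect in practice. The SAP gives no algorithm that turns a laboratory value into an adverse event. SAP 8.2 takes severity from the investigator through the CRF, and protocol section 10 requires the investigator's causality assessment. A programmed out-of-range flag would have neither. This stands: if the tables use only investigator-recorded events, there is no inflation. It does not remove the conflict, because the SAP sentence still states another rule.

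A second reply is that findings may mean examination findings. Protocol 8.1.2 names abnormal physical examination findings and abnormal laboratory values separately, and SAP 6.2 has its own heading for abnormal laboratory data. That reading is possible, but the sentence does not say so, and the protocol also uses the word for tests. Nor does the SAP keep the two apart throughout, since its list of adverse events of special interest includes a CK threshold.

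Third, the protocol's fourth criterion lets the sponsor deem a test result an adverse event. That allows additions by judgment; it does not make every finding one. The protocol's exclusion about repeating a test is also weaker support than the list of criteria, because it concerns repeat testing and not a first isolated value.

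A reader might go further and infer that incidence will be inflated, that clinically relevant events will be swamped, or that laboratory abnormalities will be double-counted. The documents do not show this. Inflation depends on literal application. SAP 8.2 summarises serious, treatment-related and special-interest events, and those leading to discontinuation, in their own right. The adverse event and laboratory tables are separate and are not added together. Larger illustrative figures, such as 1 − 0.95^11 = 43.1% for all 11 analytes, count four lipids that the drug is expected to improve as if each were equally likely to become newly abnormal.

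**Conclusion.** The conflict is real, and the SAP sentence is wrong as written. Applied literally to laboratory results, it could raise adverse event incidence through isolated out-of-range values, more so in patients with unplanned visits, and so affect the tables by dose within risk stratum. If only investigator-recorded CRF events are tabulated, it would not.

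The size cannot be derived from the documents. The range of about 7% to 30% of patients rests on assumed rates of 1% to 5%, seven independent non-lipid analytes and one post-baseline visit, and it is not a prediction. The primary endpoint is unaffected and safety is summarised descriptively without hypothesis tests, so this is a minor correction.

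**What to change.** Reconcile the two passages by replacing the SAP 6.2 sentence with: *Adverse events are those recorded by the investigator under protocol section 10; abnormal test findings are adverse events only if they meet the protocol's abnormal-test criteria.* Report other laboratory abnormalities only in the laboratory summaries of SAP 8.2.

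The cost is one SAP sentence, with no change to data collection or design. SAP 8.2 plans abnormality percentages only for CK, AST and ALT, a change-from-baseline summary for clinical laboratory data, and no shift tables. Isolated out-of-range values of other analytes would therefore not be counted in a table, which is already the case in the planned laboratory section.
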